# 5. Inclusion/Exclusion Criteria

#### Inclusion:

- 1. Parent guardian must be able to understand and provide informed consent
- 2. Subjects enrolled in Protocol NA\_00077852 "Oral Immunotherapy for Induction of Tolerance in Peanut Allergic Children" who meet at least one of the following criteria:
- a. a reaction to a cumulative dose of ≤1000 mg of peanut protein during the EndofTreatment food challenge
- b. subjects determined to be assigned to the placebo cohort **Exclusion**:

- 1. Inability or unwillingness of a parent guardian to give written informed consent or comply with study protocol
- 2. History of severe anaphylaxis to peanut, defined by severe hypoxia, hypotension, neurological compromise, confusion, cardiovascular collapse, or loss of consciousness
- 3. Significant chronic disease (other than asthma, rhinitis, or atopic dermatitis) requiring therapy; e.g., heart disease or cystic fibrosis which is judged by the investigator to have potential impact on study outcomes or safety.
- 4. Severe or poorly controlled atopic dermatitis per investigator's discretion
- 5. Past or current history of eosinophilic gastrointestinal disease
- 6. Diagnosis of asthma that meets any of the following criteria:
  - Uncontrolled asthma (as per Global Initiative for Asthma [GINA] latest guidelines)
  - History of 2 or more systemic corticosteroid courses in the last year or 1 systemic course within the 3 previous months prior to visit 1 for treating wheezing
  - Prior intubation/mechanical ventilation for asthma
- 7. Currently receiving β-blocking agents, angiotensin-converting enzyme inhibitors, angiotensin-receptor blockers, calcium channel blockers or tricyclic antidepressant therapy.
- 8. Current participation in another clinical trial or participation in another clinical trial in the last 90 days

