# **Open Label Peanut Oral Immunotherapy in Children: IMPACT Follow Up Study (IND #17784)**

# 1. Abstract

This application is being submitted as a follow-up to Protocol NA\_00077852 "Oral Immunotherapy for Induction of Tolerance in Peanut Allergic Children." The "IMPACT" protocol was a double-blind, placebo-controlled study of peanut oral immunotherapy in children 12-48 months of age. As part of the IMPACT protocol, all participants who received placebo treatment were promised the opportunity to receive open label treatment at the conclusion of the doubleblind phase and initial follow-up. At the time of submitting IMPACT, we did not specify any detailed protocol for the open label crossover treatment, as this is an evolving field, but we are now ready to offer this open label treatment as promised.

There are no specific hypotheses to be tested. The main research questions will focus on the safety and efficacy of the treatment.

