#### 2. Objectives

 The primary objectives of this protocol is to provide open label peanut oral immunotherapy (OIT) for those subjects who received placebo treatment in the doubleblind phase of the above noted study and to assess safety, as measured by the incidence of adverse events and the proportion of subjects who discontinue treatment due to adverse events.

Secondary objective will include:

2. Efficacy of the treatment, as defined by an end of treatment oral peanut challenge.

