#### 3. Background

Anaphylaxis is a severe, potentially fatal, systemic allergic reaction that occurs suddenly after contact with an allergy-causing substance. Peanut allergy affects 1-2% of US children and is associated with a high risk of life-threatening anaphylaxis. Even more concerning, peanut is the allergen most commonly associated with death and near-death following food-induced anaphylaxis and is frequently encountered in common food products. Peanut allergy also persists into adulthood in the majority of affected individuals, with less than 25% of peanutallergic children naturally developing tolerance.

Currently, treatment for peanut allergy is limited to dietary avoidance and ready access to selfinjectable epinephrine. However, immunotherapy for food allergy has been evaluated extensively over the last decade with studies focusing on oral, sublingual and epicutaneous immunotherapy to treat peanut, milk and egg allergy. When comparing these forms of immunotherapy for peanut allergy, oral immunotherapy (OIT) has proven to be the most efficacious to date.

The rationale for this study is that peanut OIT will induce immune modulation resulting in suppression of allergic responses allowing for desensitization to peanut and protection from anaphylaxis. The use of peanut flour for this study is similar to other single allergen OIT studies. The study product will be manufactured by the University of North Carolina. We have selected a dosing strategy based on all available information that is most likely to best balance safety with efficacy.

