#### 8. Risks

**OIT:** The primary risk of the study is related to the peanut OIT. Previous studies have shown that mild reactions, such as oral pruritus, are very common, while more severe respiratory or systemic reactions occur in less than 1% of doses. The dosing schema to be used on the initial escalation day followed by the build-up phase of immunotherapy is based on previous experience with peanut, egg, milk, and wheat OIT. In addition to acute reactions, 10-20% of treated subjects experience more chronic abdominal pain, which is the most common reason to discontinue treatment. Some of those subjects have eosinophilic esophagitis, which has been estimated to occur in 2-5% of children receiving OIT. Subjects who persist with symptoms consistent with eosinophilic esophagitis such as swallowing difficulty, food impaction, persistent vomiting, abdominal pain, nausea and/or heartburn beyond 4 weeks of OIT avoidance will be referred to GI.

**Oral food challenge:** Since the subjects will have already undergone an End-of-Treatment oral food challenge in the IMPACT study, a baseline food challenge will not be needed to establish a peanut allergy diagnosis. An end-of- treatment challenge will be conducted to determine safe levels of peanut to eat, but the subjects will be substantially desensitized at that time, making reactions less likely overall. However, it is important to recognize that there is still risk of a reaction that could even be severe. Common symptoms may include urticaria, angioedema, nausea, abdominal discomfort, vomiting and/or diarrhea, rhinorrhea, sneezing and/or mild wheezing. The major risks involved include severe breathing difficulties, and rarely, a drop in blood pressure. While a severe outcome is theoretically possible (i.e. death), this has only occurred once in the world in medically supervised oral food challenges. To date the primary investigator has performed more than 5000 oral food challenges without a serious lifethreatening anaphylactic reaction or need for hospitalization

Trained staff will be present to administer study food challenges and a physician will be at the bedside to provide oversight, evaluation, and treatment as needed. The risks of oral food challenges are minimized by the following procedures:

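### Placebo children can enter whatever their IMPACT challenge result, so children who no longer react can be pooled into the treatment-related safety and desensitization proportions

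*Combined protocol and SAP*

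**What the plan says.** Section 5 (Inclusion, item 2) takes subjects from the IMPACT protocol "who meet at least one of the following criteria". Criterion 2a is "a reaction to a cumulative dose of ≤1000 mg of peanut protein during the EndofTreatment food challenge". Criterion 2b is "subjects determined to be assigned to the placebo cohort". None of the eight exclusions concerns current reactivity to peanut.

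Section 8 (Oral food challenge) dispenses with a baseline challenge. Its ground is "Since the subjects will have already undergone an End-of-Treatment oral food challenge in the IMPACT study", from which it concludes that "a baseline food challenge will not be needed to establish a peanut allergy diagnosis".

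The Abstract explains where 2b comes from: "all participants who received placebo treatment were promised the opportunity to receive open label treatment". Section 2 sets the primary aim as providing that treatment and "to assess safety, as measured by the incidence of adverse events and the proportion of subjects who discontinue treatment due to adverse events". The secondary objective is efficacy, judged by an oral peanut challenge at the end of treatment. Section 7 plans descriptive statistics only, covering the proportion desensitized and measures of safety, with no breakdown by IMPACT challenge result. On natural history, Section 3 says that peanut allergy usually persists, "with less than 25% of peanutallergic children naturally developing tolerance".

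**The concern.** Section 8 treats the diagnosis as settled by a challenge whose result criterion 2b does not ask for. Having undergone a challenge is not evidence of allergy; having reacted to it is. The children joined IMPACT at 12–48 months of age, and the placebo arm went through the blinded phase without active treatment. The protocol itself accepts that some peanut-allergic children become tolerant naturally, so some placebo children may have passed.

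Those children would be in the denominator of every reported proportion while having little scope for allergic dosing reactions or for stopping because of them. They would also be expected to pass the exit challenge, which has no control arm and is not preceded by a baseline challenge in this study. The treatment-related safety figures would look better, and so would the desensitization figure, for a reason unrelated to treatment. A reader of the results could not separate the two explanations.

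**Working it through.** **Step 1. Whom 2b adds.** Criterion 2a already covers every child, from either arm, who reacted at a cumulative dose of 1000 mg or less. Beyond those, 2b adds only placebo children who (i) reacted above 1000 mg, (ii) did not react, or (iii) have no challenge result. Group (i) is allergic. Group (ii) is eligible on the text and has no demonstrated current allergy. Group (iii) is possible on the wording of 2b but is not expected (see the objection).

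**Step 2. Inputs.** The plan states no sample size and no expected event rate, so it has no figure to reproduce.

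- w, the share of entrants who are placebo children: not stated. Assumed 100% and 50%. It falls below 100% when active-arm children enter through 2a, all of whom have a documented reaction.
- f, the tolerant share among placebo entrants: not stated. Assumed 5–25%. The upper end borrows the Section 3 figure, which is a general ceiling and not an IMPACT placebo result. The true value could be close to 0.
- p, the treatment-related proportion (for example, discontinuation for allergic adverse events) in allergic children: assumed 20%. Section 8 gives 10–20%, but for chronic abdominal pain, not for discontinuation.
- Tolerant children are assumed to have no treatment-related events and to pass the exit challenge.

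**Step 3. Treatment-related safety proportion.** Reported = p(1 − wf).

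| w | f | wf | Reported at p = 20% |
|---|---|---|---|
| 100% | 5% | 0.05 | 0.20 × 0.95 = 19% |
| 100% | 25% | 0.25 | 0.20 × 0.75 = 15% |
| 50% | 5% | 0.025 | 0.20 × 0.975 = 19.5% |
| 50% | 25% | 0.125 | 0.20 × 0.875 = 17.5% |

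The relative understatement equals wf whatever p is: 5–25% at w = 100% and 2.5–12.5% at w = 50%.

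**Step 4. All-cause adverse-event incidence.** If a is the incidence in allergic children and u the incidence in tolerant children, reported = a − wf(a − u). Tolerant children still have unrelated events, so u is above 0 and the shortfall is smaller than the wf × a that full dilution would give. The documents offer no value for u.

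**Step 5. Desensitization.** If s is the success proportion in allergic children, reported = wf + (1 − wf)s. At an assumed s = 50%:

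- w = 100%: f = 5% gives 0.05 + 0.95 × 0.50 = 52.5%; f = 25% gives 0.25 + 0.75 × 0.50 = 62.5%.
- w = 50%: f = 5% gives 0.025 + 0.975 × 0.50 = 51.25%; f = 25% gives 0.125 + 0.875 × 0.50 = 56.25%.

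**The case against.** The strongest reply is that 2b does what the study was set up to do. Section 2 names placebo recipients as the target group, and the Abstract records a promise to all of them. For that group, a proportion over all treated children is a legitimate estimate and not a biased one; the bias arises only when it is read as the safety of treatment in children known to be allergic. This stands. It rules out restricting 2b to reactors and means the all-treated figures should be kept. It does not rescue the Section 8 statement that diagnosis is established, or the absence of any breakdown by challenge result.

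A reader might also infer that children who left IMPACT before its End-of-Treatment challenge will be enrolled. The documents do not support that as an expectation. The Abstract places the offer after the blinded phase and initial follow-up, Section 4 takes consent at the last IMPACT visit or afterwards, and Section 8 says subjects will have had the challenge. Completion is presumed throughout. It is just not written as an entry condition.

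A reader might further infer that both primary safety proportions are understated by 5–25%. That range applies only to treatment-related events, only if every entrant is a placebo child, and only at the assumed f. All-cause incidence moves less.

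Finally, no hypothesis is tested and the analysis is descriptive. If 20 children were treated (an assumption), one child is 5 percentage points, so the shifts of 0.5–5 points in Step 3 amount to at most one child. This also stands, and limits how much weight the point can carry.

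**Conclusion.** The point holds as a gap between Sections 5 and 8 with a reporting consequence. As written, the plan can treat placebo children who passed the IMPACT challenge, pool them into the treatment-related adverse-event and discontinuation proportions, and count them as desensitized at exit. The direction is clear: safety looks better and efficacy looks higher than in children with demonstrated allergy.

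The size is not known. On the stated assumptions, a treatment-related proportion of 20% would be reported as 15–19% if all entrants are placebo children and as 17.5–19.5% if half are. If no placebo child passed, the effect is nil. No test or formal decision depends on it. It is worth correcting because the correction is cheap and the IMPACT results should already be held.

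**What to change.** Keep enrolment open to all placebo recipients, as promised. In Section 7, add the following:

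- Classify each child, from existing IMPACT records and before outcomes are summarized, by End-of-Treatment challenge status: reacted, passed or not done.
- Report safety and exit-challenge results by that status.
- Give the treatment-related safety proportions and the desensitization proportion for documented reactors alongside those for all treated subjects, each with its denominator.

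Reconcile Section 8 with criterion 2b, so that the text no longer treats the diagnosis as established for children whose challenge result is not an entry requirement.

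The cost is one classification variable, one added set of table columns and one corrected statement, with no new procedure for any child. The downside is a smaller denominator for the reactor figures and, if any placebo child did pass, slightly less favourable results.

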### 6. Drugs/ Substances/ Devices

The treatment agent, a de-fatted peanut flour, will be provided by the University of North Carolina (UNC) GMP manufacturing facility under an Investigational New Drug (IND) application to the FDA. All study product will be obtained from the same manufacturer; a certificate of analysis obtained according to FDA standards will be stored as per manufacturer's recommendations to ensure stability. Research staff will administer food flour to the subject orally in an appropriate age-appropriate food vehicle. Each peanut flour/powder is weighed into a separate container to be dispensed to the subject. Dosage will be done according to the protocol as set forth above. For home administration, the family will be provided with an adequate supply of individually packaged peanut OIT. The powder may be added to apple juice, milk, applesauce, pudding or other age-appropriate food. The product must be consumed promptly after mixing. If there is a prolonged delay in consumption (>2 hours), the product should be discarded and a new product package mixed and consumed. Subjects or their parents will be instructed to take/administer the dose of OIT at approximately the same time of the day each day. At least approximately 12 hours should pass between doses.

Drug Accountability: Under Title 21 of the Code of Federal Regulations (21CFR §312.62) the investigator is required to maintain adequate records of the disposition of the investigational agent, including the date and quantity of the drug received, to whom the drug was dispensed (subject-by-subject accounting), and a detailed accounting of any drug accidentally or deliberately destroyed. Records for receipt, storage, use, and disposition will be maintained by the study sites. A drug-dispensing log will be kept current for each subject. This log will contain the identification of each subject and the date, lot and quantity of drugs dispensed. All records

regarding the disposition of the investigational products will be available for inspection by the IRB and FDA.

### 7. Study Statistics

As an open label follow-on study, statistics will be purely descriptive, describing the proportion of subjects achieving desensitization as well as measures of safety.

**Early stopping rules:** Study enrollment and treatment will be suspended pending expedited review of all pertinent data by the IRB and FDA if the following occur:

- Any death.
- More than one severe anaphylactic reaction related to peanut immunotherapy dosing at any stage of the protocol.
- More than three subjects require 2 or more injections of epinephrine to treat one allergic adverse event during peanut OIT dosing.
- More than 3 subjects require epinephrine on 2 or more occasions to treat dosingrelated reaction over the course of the study

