Subjects who experience dose limiting symptoms during an up-dosing visit will continue on the previously tolerated dose for an additional 2 weeks. Subjects who experience dose limiting symptoms with a home dose will be seen in the research unit for down-dosing to the last tolerated dose. Subjects will remain on the last tolerated dose for at least 2 weeks before attempting another up-dosing. A subject may attempt a specific dose level 3 separate times before the dose is considered "not tolerated". In that case, the dose previously tolerated will become the maintenance dose and the subject will not attempt additional up-dosing.

Dose Build-Up Schedule				
Dose #	Peanut protein	Interval (weeks)	% Increase	
5	10 mg	2	66%	
6	20 mg	2	100%	
7	30 mg	2	66%	
8	50 mg	2	60%	
9	75 mg	2	33%	
10	125 mg	2	60%	
11	200 mg	2	62.5%	
12	300 mg	2	33%	
13	500 mg	2	60%	
14	750 mg	2	50%	
15	1000 mg	2	25%	

Consent will be obtained at the last visit in IMPACT Study. For subjects who have already completed the last visit of that protocol and/or families who request additional time to review the consent, consent will be obtained at the 1st visit in the Pediatric Clinical Research Unit prior to

any research specific procedures. The study will be explained in age appropriate terms to the participants and they will be given the opportunity to ask questions. Some of the older subjects may have some context to comprehend the assent process. The assent process will be documented in the clinical note.

At each dosing visit, the following procedures will be performed prior to dose administration:

- Vital signs
- Review of adverse events including any accidental exposure to peanut
- Review of concomitant medications
- Review of home dosing diaries
- Physical exam
- Peak flow

The build-up phase will comprise up to 22-52 weeks. Subjects will then enter the Maintenance phase and will continue on daily OIT at the maximum tolerated dose established during the Build-up phase. The Maintenance phase will consist of at least 12 weeks and may continue as long as through week 64. Subjects will be seen every 6-8 weeks during the Maintenance phase. The window between maintenance visits may be extended to longer than 6-8 weeks if necessary. At the end of the Maintenance phase, subjects will undergo an open peanut oral food challenge to a maximum of 4000 mg of peanut protein using the following dosing regimen:

Dose #	Peanut Protein (mg)	Cumulative Dose (mg)
1	100	100
2	300	400
3	600	1000
4	1000	2000

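### Section 7 reports efficacy only as an exit proportion with no dose threshold and plans no comparison with each child's IMPACT End-of-Treatment challenge, so children already tolerant at entry cannot be told apart from children who converted

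*Combined protocol and SAP*

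**What the plan says.** Section 2 makes efficacy the secondary objective: "Efficacy of the treatment, as defined by an end of treatment oral peanut challenge". Section 7 says how it will be reported: "As an open label follow-on study, statistics will be purely descriptive", the content being "describing the proportion of subjects achieving desensitization as well as measures of safety". Section 1 adds "There are no specific hypotheses to be tested". No section gives the tolerated dose that counts as desensitization.

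The exit assessment in Section 4 is "an open peanut oral food challenge to a maximum of 4000 mg of peanut protein", given in five steps. No challenge is done at entry. Section 8 explains why: "Since the subjects will have already undergone an End-of-Treatment oral food challenge in the IMPACT study", a new one is not needed to establish the diagnosis.

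The IMPACT result is also read for eligibility. Section 5 requires at least one of two criteria. Criterion 2a is "a reaction to a cumulative dose of ≤1000 mg of peanut protein during the EndofTreatment food challenge". Criterion 2b is assignment to the IMPACT placebo cohort, with no condition on the challenge result. No exclusion criterion removes a child who tolerated that challenge.

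**The concern.** The IMPACT challenge stands in for a baseline in the design and at eligibility, and then has no place in the analysis. An exit proportion alone describes status at exit. In a single-arm study it does not show how many children moved from reactive to tolerant while on treatment.

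This matters because of criterion 2b. Sections 1 and 2 present placebo children as the population the study is meant to serve, so 2b is the main entry route, and it sets no reactivity limit. A placebo child who could already eat more than 1000 mg would be counted with the children who gained that ability. Criterion 2a is not restricted by arm, so it can also bring in actively treated children, whose IMPACT result has a different meaning. A single pooled exit figure mixes these starting points. What is at stake is how the secondary efficacy result can be read.

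**Working it through.** **Exit dose ladder (Section 4).** The doses are 100, 300, 600, 1000 and 2000 mg. The running sums are 100, 100 + 300 = 400, 400 + 600 = 1000, 1000 + 1000 = 2000, and 2000 + 2000 = 4000 mg. They match the table. The 1000 mg limit in criterion 2a falls on the third step, so a comparison at that point is feasible. The plan gives no sample size, expected rate or precision target, so there is no other figure to reproduce.

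**Who could already have tolerated more than 1000 mg (Section 5).**

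- Active arm, entering under 2a: reacted at 1000 mg or less, so no.
- Placebo arm, meeting both 2a and 2b: reacted at 1000 mg or less, so no.
- Placebo arm, meeting 2b alone: result not restricted, so possible.

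For a threshold above 1000 mg, only the third group can contribute. If the threshold were lower, for example 400 mg, some 2a children could also have met it at entry. The undefined threshold and the missing comparison are therefore linked.

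**Size.** Let f be the share of all children who already met the threshold in IMPACT, and g the proportion meeting it at exit among the rest. Assume that those who met it at entry still meet it at exit.

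- Exit proportion: E = f + (1 − f)g
- Converted, as a share of all children: C = (1 − f)g
- Difference: E − C = f, whatever g is

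The documents give neither f nor g. With g assumed to be 50%:

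| f (assumed) | E | C | E − C |
|---|---|---|---|
| 0 | 50% | 50% | 0 points |
| 10% | 0.10 + 0.90 × 0.50 = 55% | 45% | 10 points |
| 20% | 0.20 + 0.80 × 0.50 = 60% | 40% | 20 points |

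With g = 0, meaning that nobody converts, E still equals f.

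**In counts, with f = 20% and exact (Clopper-Pearson) 95% intervals; N is assumed.**

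- N = 20: 4 already tolerant and 12/20 at exit (60%; 36% to 81%). Among the 16 reactive at entry, 12 − 4 = 8 converted (8/16 = 50%; 25% to 75%).
- N = 50: 10 already tolerant and 30/50 at exit (60%; 45% to 74%). Among the 40 reactive at entry, 30 − 10 = 20 converted (20/40 = 50%; 34% to 66%).

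Only the exit figure is planned. It takes the same value under many combinations of f and g.

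**The case against.** The strongest reply is that the problem may be empty. Every child who met 2a reacted at 1000 mg or less. Section 8 treats the IMPACT challenge as having settled the diagnosis, which suggests that reactive children were expected. If no 2b-only child tolerated more than 1000 mg, then f = 0 and the exit and converted proportions coincide for any threshold above 1000 mg. This stands as a limit on size. It does not remove the point, because 2b permits such a child and the plan would not show whether there were any.

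A second reply is that the study delivers promised crossover treatment, puts safety first and tests nothing. That also stands and confines the consequence to the secondary result. It is no reason to leave the comparison out, because a paired listing is itself descriptive.

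A third is that the IMPACT challenge is an imperfect baseline. It precedes entry by an interval that is not stated, since Section 1 places the crossover after an initial follow-up. Its steps, ceiling and blinding are not in these documents. For any active-arm child it was an on-treatment result. These limits stand and shape the fix.

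Four stronger readings are tempting, and the documents do not support them:

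- A reader might say that change on treatment is never measured. Both challenges exist; what is missing is a planned comparison.
- A reader might say that the five steps are collapsed to pass or fail. Section 7 does not say so. It names a proportion without defining it, and Sections 4 and 8 also use the challenge outcome for individual dietary guidance.
- A reader might take "less than 25% of peanutallergic children naturally developing tolerance" in Section 3 as the baseline tolerance rate and subtract up to 25 points from the exit figure. That is a statement about natural history in peanut-allergic children, not a result of the IMPACT challenge in those who enrol here.
- A reader might expect a paired comparison to establish that treatment works. With no concurrent control, the change would still include natural resolution.

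**Conclusion.** The point holds as a gap in the planned analysis. Efficacy is an exit proportion with no stated threshold, and the challenge result that the protocol relies on for diagnosis and eligibility is not used to interpret it. The exit proportion exceeds the converted proportion by the share already tolerant at entry, provided those children remain tolerant at exit. That share is unknown and possibly zero. For thresholds above 1000 mg it cannot exceed the share of children who entered under 2b alone. The 10- and 20-point differences shown are illustrations on assumed values, not estimates for this trial. The change is worth making because the entry result should already be on file.

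**What to change.** In Section 7:

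1. State the cumulative tolerated dose at the exit challenge that counts as desensitization for analysis.
2. List, for each child, the IMPACT End-of-Treatment tolerated dose, the date of that challenge, the IMPACT arm and the entry criterion (2a or 2b), beside the exit tolerated dose. Give IMPACT doses as recorded, without mapping them to the nearest exit step.
3. Among children who reacted at a cumulative dose of 1000 mg or less in IMPACT, report the proportion tolerating more than 1000 mg at exit. For all children, report the proportion tolerating 4000 mg. Give exact 95% confidence intervals for both, separately by IMPACT arm and entry criterion, so that on-treatment and placebo baselines are not pooled.
4. Keep children with no IMPACT result in the exit proportion, marked as baseline not available.

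The cost is a few existing items per child from the IMPACT record, plus one listing and one table. No new procedure or test is needed. Some groups may be small and their intervals wide. Section 7 should also say that the comparison is descriptive only, because of the unstated gap between challenges, possible differences in steps or blinding, the on-treatment status of any active-arm child's IMPACT result, and the lack of a concurrent control.
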